7.3 Other Study Variables

Other study variables of interest are as follows:

- age
- sex
- race
- height
- dry weight
- Tanner stage
- PTH (pg/mL)
- corrected calcium (mg/dL)
- phosphorus (mg/dL)
- phosphate binder use (yes/no) and dates of use
- vitamin D sterol use (yes/no) and dates of use

8. TIME AT RISK FROM EXPOSURE

Patients accumulate time at risk (either exposed or unexposed) from the study time of start of follow-up until death, censored, or transplanted.

9. POTENTIAL SOURCES OF BIAS IN STUDY

There are 2 key potential sources of bias in this study.

9.1 Confounding by Indication and Information Bias

Confounding by indication and information bias have the potential to adversely affect the validity of any comparison between cinacalcet users and nonusers in this study.

Specifically, differences in the frequency of safety events may be attributed to cinacalcet use when, in fact, they are indicative of either:

Approved

- underlying differences in risk factors between patients receiving and not receiving cinacalcet (confounding by indication)
- differential capture of safety data by cinacalcet use (information bias)

An example of the former would be if patients receiving cinacalcet are less likely to have a history of seizures (due to perceived safety concerns about cinacalcet and seizure risk), or if cinacalcet use is associated with a higher underlying disease severity.

Differential capture/missingness could occur if physicians were more diligent in recording hospitalization events for their cinacalcet patients, due to higher vigilance around use of off-label therapy (information bias).

In either of the aforementioned scenarios, the frequency of events for cinacalcet treated patients would appear spuriously higher than for untreated patients.

There may be misclassification in the NAPRTCS-generated summary table of cinacalcet users and users, as any use of cinacalcet will define cinacalcet exposed in the table. Start and stop dates of time of cinacalcet use, however, will be collected, and appropriate linkage between treatment window and events will be reported.

9.2 Ascertainment of Adverse Events of Special Interest Bias

In addition, ascertainment of the AESI is made solely by the individual physicians treating his/her patients. While determination of the occurrence of seizures and infections requiring hospitalization may appear to be more straightforward, NAPRTCS does not have a registry wide definition of hypocalcemia. Each physician entering data into the registry uses his/her individual judgment.

10. REMOVAL AND REPLACEMENT OF SUBJECTS

Since this study is based upon real-life clinical practice, data from all enrolled patients will be collected. There will be no specific procedures for removal and replacement of patients.

11. SAFETY DATA COLLECTION, RECORDING, AND REPORTING

This study is based upon data from a single database registry. Amgen will not collect data directly from patients, and all AESI reports will be obtained from the NAPRTCS registry. All data are collected by NAPRTCS through retrospective chart review, and reports will be provided to Amgen annually. Upon receipt of this annual report, Amgen will provide this information to regulatory agencies.

Approved

12. SAMPLE SIZE CONSIDERATIONS

The expected number of patients to be enrolled (during the years 2012 to 2015) is estimated to be between 1000 to 1500, with approximately 200 to 300 of these patients likely to receive cinacalcet over the life of the study. The objective of the study is to describe demographic characteristics, laboratory values, and events of interest (hypocalcemia, seizures, or infections requiring hospitalization) for patients in this population who do or do not receive treatment with cinacalcet.

The background rate of hypocalcemia and seizures is <1%. The rate of infection is expected to be higher, as infections are more common in the pediatric population.

Table 1 below illustrates the half-width of 95% confidence intervals for events with varying incidence rates, stratified by the expected number of cinacalcet (N = 300) and non-cinacalcet (N = 1200) patients:

Table 1. Confidence Intervals for Event Probabilities

N	True Probability of Event	95% CI Half-width
1200	0.1	0.017
1200	0.05	0.012
1200	0.01	0.006
1200	0.005	0.004
300	0.1	0.034
300	0.05	0.025
300	0.01	0.011
300	0.005	0.008

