13.2 Planned Methods of Analysis

Descriptive analyses will consist of summary statistics: mean, standard deviation, standard error, minimum, maximum, median, and quartiles for continuous variables, and frequency and percent for categorical variables.

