14. STRENGTHS AND LIMITATIONS

Potential strengths (advantages) of the study include the following:

- utilization of the largest registry in North America for pediatric patients on dialysis
- prospective design allows for contemporary assessment of practice patterns
- utilizes existing data that are routinely collected from clinical practice settings reducing cost/burden on investigators and patients
- findings from this study may be evaluated collectively with those from other clinical studies conducted in other countries to complement a comprehensive global pediatric program to evaluate safety and efficacy

Potential limitations (disadvantages) of the proposed study include:

- small sample size due to the low prevalence of dialysis dependent CKD pediatric patients (estimated 2000 point prevalent patients in the United States)
- estimated event counts will be low or very low for rare AESIs
- voluntary nature of data entry into the NAPRTCS registry, which may result in missing data and information bias

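### Table 1's symmetric 95% half-widths for rare events in 300 cinacalcet patients do not describe 95% intervals, and they understate the upper limit by 0.7 to 0.8 percentage points

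*Protocol*

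**What the plan says.** Protocol Section 12 expects 1000 to 1500 patients, with "approximately 200 to 300 of these patients likely to receive cinacalcet over the life of the study". It then states that "The background rate of hypocalcemia and seizures is <1" per cent and expects infections to be more frequent. Its only statement of precision is Table 1, introduced with "Table 1 below illustrates the half-width of 95% confidence intervals for events with varying incidence rates" and "stratified by the expected number of cinacalcet (N = 300) and non-cinacalcet (N = 1200) patients". For N=300 the table prints half-widths of 0.034, 0.025, 0.011 and 0.008 at true probabilities 0.1, 0.05, 0.01 and 0.005. It names no formula.

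Section 13.2 plans descriptive summaries, with "frequency and percent for categorical variables"; it names no confidence interval method. Section 14 concedes among the limitations that "estimated event counts will be low or very low for rare AESIs", without linking this to Table 1.

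**The concern.** In the last two N=300 rows the half-width is larger than the probability it belongs to: 0.011 around 0.01, and 0.008 around 0.005. Read as p plus or minus the half-width, the lower limits are negative. A probability cannot be negative, so a single symmetric number cannot describe a 95% interval there.

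The protocol's own background rate points to these two rows for hypocalcemia and seizures. In a descriptive study without hypothesis tests, precision is all that the sample size section can offer. The upper limit is the informative end for a safety event, because it says how large a risk the data could leave unexcluded. If it is set too low, the reader, including the regulators who receive the reports, expects more reassurance from 300 treated patients than they can give.

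**Working it through.** **Inputs (Protocol Section 12).** 95% two-sided, z=1.96; N=300 and N=1200; p=0.1, 0.05, 0.01, 0.005.

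**1. Reproducing Table 1.** Half-width = 1.96·√(p(1−p)/N).

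| N | p | Computed | Printed | Exact coverage of the Wald interval |
|---|---|---|---|---|
| 1200 | 0.1 | 0.0170 | 0.017 | 94.4% |
| 1200 | 0.05 | 0.0123 | 0.012 | 95.0% |
| 1200 | 0.01 | 0.0056 | 0.006 | 94.4% |
| 1200 | 0.005 | 0.0040 | 0.004 | 93.5% |
| 300 | 0.1 | 0.0339 | 0.034 | 93.8% |
| 300 | 0.05 | 0.0247 | 0.025 | 92.6% |
| 300 | 0.01 | 0.0113 | 0.011 | 79.9% |
| 300 | 0.005 | 0.0080 | 0.008 | 77.7% |

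All eight match. In the last two rows neither a continuity-corrected Wald (0.0129, 0.0097), a Wilson (0.0128, 0.0101) nor a Clopper-Pearson half-width (0.0134, 0.0104), the last two taken at the expected count, would give the printed figures.

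Coverage is the sum of Binomial(N, p) probabilities over those counts whose Wald interval contains p.

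**2. Implied limits at N=300.**
- p=0.01: 300 × 0.01 = 3 expected events; 0.01 ± 0.0113 gives −0.0013 to 0.0213.
- p=0.005: 300 × 0.005 = 1.5 expected events; 0.005 ± 0.0080 gives −0.0030 to 0.0130.

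**3. Why coverage fails.**
- p=0.005: the chance of no event is 0.995³⁰⁰ = 0.222. The Wald interval is then 0 to 0 and misses the truth, which explains almost all of the shortfall to 77.7%.
- It worsens further down: coverage is 59.4% at p=0.003, where 0.997³⁰⁰ = 0.406.
- p=0.01: with one event the Wald upper limit is 0.00986, just under 0.01. Zero and one event therefore both miss: 0.0490 + 0.1486 = 0.198. At p=0.0098 one event is enough to cover, and coverage is 94.5%. The 79.9% is thus a knife-edge value and not typical of rates near 1%. In between, coverage is 93.2% at p=0.009 and 87.7% at p=0.007.

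**4. Size of the error.** Clopper-Pearson limits averaged over Binomial(300, p):

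| p | Mean exact half-width | Table 1 (unrounded) | Shortfall | Mean exact upper limit | Upper limit implied by Table 1 |
|---|---|---|---|---|---|
| 0.01 | 0.0130 | 0.0113 | 0.0018 | 2.86% | 2.13% |
| 0.005 | 0.0100 | 0.0080 | 0.0021 | 2.09% | 1.30% |

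Shortfalls are taken before rounding. The upper limit is understated by 2.86 − 2.13 = 0.73 and 2.09 − 1.30 = 0.79 percentage points. Against Wilson intervals the mean half-widths are 0.0125 and 0.0098, so the shortfall is slightly smaller (0.0012 and 0.0018).

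**5. Exact 95% limits by observed count, N=300.**

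| Events | Lower | Upper |
|---|---|---|
| 0 | 0 | 1.2% |
| 1 | 0.01% | 1.8% |
| 2 | 0.08% | 2.4% |
| 3 | 0.2% | 2.9% |

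**6. Lower end of the protocol's own range.** With 200 cinacalcet patients the Wald half-widths would be 0.0138 and 0.0098, with coverage of 86.5% at p=0.01 and 63.3% at p=0.005.

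**The case against.** The other side has several good points.

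- **The arithmetic is right.** A reader might infer from the negative limits that Table 1 was miscalculated. It was not: every entry is correct for the Wald formula. What is wrong is putting a 95% label on that formula at 1.5 to 3 expected events.
- **The table prints half-widths, not limits.** The negative limits appear only when the half-width is centred on p, and a half-width above p already signals poor precision. This is fair, but a half-width has no other use than to be added and subtracted, and at the upper end it misleads without looking odd.
- **Like for like, the error is about 0.002, and Clopper-Pearson is conservative** (98.9% and 98.2% coverage in these rows). Both are true. Wilson, with 96.7% and 93.5%, gives nearly the same upper limit: 2.9% at three events by either method.
- **Coverage of 78 to 80% is not a general property.** A reader might take it as the behaviour for any event near 1%. It is not, because the p=0.01 figure is a knife-edge value. Only the p=0.005 figure and the decline below it are robust.
- **No reported interval is affected.** A reader might infer that the safety reports will carry faulty intervals. The protocol does not support this: Section 13 plans rates and descriptive summaries and names no interval method. That choice can be left to the analysis plan.
- **No decision hangs on the table.** Every eligible registry patient is included, so N does not come from Table 1, and Section 14 discloses low event counts. This limits the consequence, but it neither corrects the two rows nor makes their 95% label true.
- **The rate below 1% is a background rate.** The protocol does not say that it applies to cinacalcet patients, and Section 7.2 counts hypocalcemia by several laboratory thresholds, some of which may be met more often. This stands as an assumption.

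**Conclusion.** Two of the eight rows of Table 1 are wrong as statements of 95% precision: N=300 with p=0.01 and with p=0.005. The practical error is moderate: about 0.002 in half-width (roughly 14% and 21% of the mean exact value) and 0.7 to 0.8 percentage points at the upper limit. The coverage failure is clear at p=0.005 and grows at lower rates; at p=0.01 it depends on the exact value chosen. The other six rows can stand at their printed probabilities, with coverage of 92.6% to 95.0%.

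The conclusion assumes independent patients, each counted once as having the event or not, the protocol's N=300, and that the background rate below 1% is a fair guide for treated patients. If hypocalcemia proves much more frequent, the point applies mainly to seizures. Because the study is descriptive and its size is set by the registry, this is a correction worth making to the stated precision, not a threat to the study's validity.

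**What to change.** In Section 12, Table 1, replace the half-width in the N=300 rows for p=0.01 and p=0.005 with separate lower and upper 95% limits from an exact (Clopper-Pearson) or Wilson method, and name the method under the table. Averaged over the binomial, the exact limits are about 0.3% to 2.9% at p=0.01 (lower limit 0.0286 − 2 × 0.0130 ≈ 0.0025, from unrounded values) and about 0.1% to 2.1% at p=0.005 (0.0209 − 2 × 0.0100 ≈ 0.0008). Since 1.5 events cannot be observed, the list by observed count (0, 1, 2 and 3 events) is the clearer display and could serve in place of both rows. The other six rows need no change.

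The cost is two recomputed rows and one line naming the method. The stated precision for rare events becomes slightly less favourable. No patients, data or analyses are added.

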13. STATISTICAL ANALYSIS

13.1 Data Collection and Management

Data for this study will be collected and managed solely by the NAPRTCS registry, and there will be no data editing required.

13.1.1 Descriptive Analyses

Since the study is descriptive in nature, the analyses will describe the study population and outcomes in all study cohorts, for age < 21 years, for age < 18 years, as well as in different follow-up time periods (before and after cinacalcet exposure). This will include the following:

Approved

- total number of patients and total number of patient-years observation based on the annual data reporting periods, and for the cumulative 3-year study period
- estimation of rates of cinacalcet use based on the annual data reporting periods, and for the cumulative 3-year study period
- estimation of rates of AESI based on the annual data reporting periods, and for the cumulative 3-year study period
- proportion of patients who received at least 1 dose of cinacalcet within 7 days preceding an episode of hypocalcemia (from amongst all patients who developed hypocalcemia)

In addition, the following descriptive analyses using summary statistics will also be conducted:

- a tabular summary (eg, frequency, percent, rate) of categorical baseline demographic and clinical characteristics by cinacalcet-exposed and cinacalcet-unexposed
- for continuous variables (eg, age, weight, laboratory values) summary statistics for measures of central tendency (mean, median, SD, Q1, Q3, min, max) will be provided by cinacalcet-exposed and cinacalcet-unexposed

The cinacalcet utilization pattern will also be assessed (eg, dosing, duration of treatment).

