Objectives: Describe the demographics, laboratory values, and secondary hyperparathyroidism (SHPT) medication use (specifically cinacalcet), and the occurrence of hypocalcemia, seizures, and infections (requiring hospitalization), in cinacalcet treated and untreated patients enrolled in the North American Pediatric Renal Trials and Collaborative Studies (NAPRTCS) receiving dialysis for chronic kidney disease (CKD).

Hypotheses: Patient characteristics, overall and for cinacalcet treated and untreated patients, will be described; the rate of hypocalcemia, seizure, and infection (requiring hospitalization) events will be estimated separately in cinacalcet treated and untreated patients enrolled in NAPRTCS.

Variables of Interest: Parameters of interest include: Age, height, dry weight, Tanner stage, sex, race, cinacalcet use (yes/no), cinacalcet start/stop dates, cinacalcet dose (mg), parathyroid hormone (PTH) (pg/mL), corrected calcium (mg/dL), phosphorus (mg/dL), phosphate binder use (yes/no), vitamin D sterol use (yes/no), hypocalcemia (yes/no), seizures (yes/no), and infections requiring hospitalization (yes/no).

Study Design: The NAPRTCS registry is a prospective, observational study of patients with CKD. This protocol will collect and tabulate a specific set of information from the NAPRTCS registry. Specifically, dialysis registry patients will be included and followed for up to three years, or for six semiannual data collection intervals. Patients will be censored at three years, transplant, death, loss to follow-up, or if no longer participating in NAPRTCS, whichever occurs first.

Sample Size: Estimated to be approximately between 1000 to 1500 patients over 3 years

Summary of Patient Eligibility Criteria: All pediatric patients < 21 years old receiving maintenance dialysis (hemodialysis or peritoneal dialysis) at a NAPRTCS affiliated center are eligible. Patients who are participating in an Amgen clinical study are ineligible. For a full list of eligibility criteria, please refer to [Section 4.4](#).

[figure not shown]
Procedures: In this prospective, observational, noninterventional registry, physicians will continue to treat their pediatric dialysis patients as per standard medical care. There are no specific study procedures required by this protocol.

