4.5 Study Period and Follow-up

Data to be included in the report will be from a time period of approximately 3 years, from July 2012 to July 2015.

The start of time at risk (index date) will begin at the time of each eligible patient's entry into the NAPRTCS registry.

Patients will be followed from study start until death, transplant, withdrawal, transfer to a nonparticipating facility, or end of the study period.

The primary completion date is defined as 01 July 2015.

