7. DEFINITION OF EXPOSURE, OUTCOME, AND OTHER STUDY VARIABLES

7.1 Exposure

The exposure is defined as cinacalcet therapy. Patients are considered exposed for the duration from start to stop date of receiving cinacalcet, and for 7 days afterwards.

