7.2 Variables of Interest

Variables of interest for this study are as follows:

- cinacalcet prescription start and stop dates
- dose of cinacalcet (mg)
- occurrence and date of seizures
- occurrence and date of infections requiring hospitalization
- occurrence and date of hypocalcemia (defined as corrected serum calcium below the age-appropriate lower limit of normal range), and categorically < 9.0 mg/dL

Approved

(patients 0 to < 2 years), < 8.4 mg/dL (patients 2 to 6 years), < 8.0 mg/dL, < 7.5 mg/dL, and < 7.0 mg/dL among subjects who are treated with or without cinacalcet

- occurrence and date of hypocalcemia (as defined by investigator) requiring treatment and action(s) taken

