13.4 Annual Analysis

Annual reports from NAPRTCS are planned for this study. For each prespecified analysis, NAPRTCS will generate a report based on the available data in the annual

Approved

data reporting period, and cumulative for the entire 3 year study period. The analysis will be limited to the analyses described in [Section 13](#).

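### Duration of cinacalcet treatment has only plain summary statistics as its named method although follow-up is censored, so on that reading the median would run low (minor, descriptive point)

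*Protocol*

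**What the plan says.** Section 13.1.1 lists duration of treatment as an example of what the utilization description will cover: "The cinacalcet utilization pattern will also be assessed (eg, dosing, duration of treatment"). It gives no statistic and no rule for a course that is still running when observation stops.

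Section 13.2 then names the methods: "Descriptive analyses will consist of summary statistics: mean, standard deviation, standard error, minimum, maximum, median, and quartiles for continuous variables". Section 13.4 adds, for the annual reports, "The analysis will be limited to the analyses described in" Section 13. No censoring-aware estimator appears anywhere in Section 13.

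Follow-up is limited. The synopsis states "Patients will be censored at three years, transplant, death, loss to follow-up, or if no longer participating in NAPRTCS, whichever occurs first". Section 4.5 says "Patients will be followed from study start until death, transplant, withdrawal, transfer to a nonparticipating facility, or end of the study period" and "Data to be included in the report will be from a time period of approximately 3 years, from July 2012 to July 2015".

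The dates to be collected are "cinacalcet prescription start and stop dates" (Section 7.2). Section 7.1 uses them to define exposed time: "Patients are considered exposed for the duration from start to stop date of receiving cinacalcet, and for 7 days afterwards". That rule classifies person-time; it does not define a duration statistic.

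**The concern.** Duration of treatment is right-censored. A child still on cinacalcet at transplant, at loss to follow-up or in July 2015 has a start date but no stop date. A plain mean or median can handle that course in two ways. It can cut the course at the last observation and count it as complete, or it can leave the course out, so that mainly early stoppers remain. Both give a result that is too short for courses starting inside the window.

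Section 3.1 gives the purpose as informing on cinacalcet use in practice, so utilization is not incidental. Section 13.4 calls for results by annual period and cumulatively, and Section 11 has the sponsor pass the annual reports to regulators. A statistic that lengthens because the window lengthens could be taken for a change in prescribing.

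**Working it through.** **Plan's own figure.** There is none for duration. The protocol's only computed figures are the confidence interval half-widths in Table 1. These reproduce (for example 1.96 × √(0.1 × 0.9 / 1200) = 0.017) and do not bear on this point.

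**Inputs.** From the protocol: a window of W = 36 months and the censoring events. Assumed, because the protocol gives no figures: new courses start evenly over the window; treatment duration is exponential with rate λ = ln 2 / median; loss, transplant or death is exponential with mean 12 to 48 months (rate c) and independent of stopping.

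**Formulae.** Let r = λ + c. The cut span exceeds t with probability (1 − t/W) × exp(−rt), and the plain median solves (1 − t/W) × exp(−rt) = 0.5. The mean cut span is (1/r) × [1 − (1 − exp(−rW)) / (rW)]. The share of courses that stop under observation is λ times that mean. In this model the relative shortfall of the mean therefore equals the share of courses still ongoing.

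**Worked case, true median 12 months, mean time to loss 12 months.** λ = 0.0578, c = 0.0833, r = 0.1411. At t = 4.07: (1 − 4.07/36) × exp(−0.574) = 0.887 × 0.563 = 0.50. The plain median is 4.1 months. The mean cut span is 7.09 × (1 − 0.196) = 5.70 months, so 0.0578 × 5.70 = 33% stop and 67% are ongoing.

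**New users, 36-month window, mean time to loss 12 to 48 months** (closed form, agrees with simulation):

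| Assumed true median | Ongoing at end | Plain median, courses cut | Share of true median |
|---|---|---|---|
| 6 months | 32–50% | 3.0–4.2 months | 50–70% |
| 12 months | 51–67% | 4.1–6.3 months | 34–53% |
| 24 months | 69–81% | 4.9–8.5 months | 20–35% |

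If ongoing courses are dropped instead, a true median of 12 months gives 3.9 to 5.7 months.

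**Short use.** With a true mean of 0.25 years and a loss rate of 0 to 0.4 per year, 8–16% of courses are ongoing, and the plain mean is 0.23 to 0.21 years. The bias is small.

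**Drift between reports.** With W = 12 and a true median of 12 months, the plain median is 2.9 to 3.9 months, against 4.1 to 6.3 at W = 36. Practice is identical in both.

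**Patients already on drug in July 2012.** Simulation with earlier starters added, true median 12 months: the plain median is 4.9 to 8.8 months with true start dates, and 4.2 to 6.9 if time is cut at the window start. The mean behaves differently. For a true mean of 1 year and a loss rate of 0 to 0.4 per year, it is 1.00 to 0.83 years with true start dates, and 0.75 to 0.58 if cut at the window start.

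**Does Kaplan-Meier repair it?** In new users, over the 36-month window, it recovers the true median. With earlier starters and no late entry it runs high, at 14 to 16 months for a true 12. With late entry it returns to about 12.

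**The case against.** The strongest reply is that the defect is inferred. A reader might conclude that the protocol prescribes means and medians of start-to-stop spans for duration. It does not. Duration is an example inside a sentence about utilization, separate from the item on continuous variables, and the start-to-stop rule belongs to the exposure definition. Section 13.2 is also not exhaustive, since 13.1.1 plans patient-years and event rates that 13.2 does not mention. Handling of ongoing courses is often left to an analysis plan, which is not shown here, and Section 17.2 has the sponsor approve the methods before reports are generated.

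Much of that stands, and it lowers the weight of the point. It does not remove it. The issue is not missing detail: the one method named for continuous variables does not suit a censored quantity, and the annual reports are confined to Section 13.

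A second reply is that patients already on treatment offset the shortfall. For the mean this can happen, but one bias then cancels another by chance. The median stayed low in the scenarios run.

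A third reply is that observed treatment time is a legitimate descriptive quantity. That is correct, provided it is labelled as such.

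**Conclusion.** The point holds as a minor one. Sections 13.1.1 and 13.2 read together would apply plain summaries to censored courses, and the median would then understate duration and drift upward over the reports.

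The size is conditional. It is small if use is short. In new users, the plain median is roughly half or less of the true median when that is assumed to be 12 months or more. These figures rest on exponential durations, even starts and independent loss, none of which is in the protocol.

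A reader might go further and say that the reported duration simply measures the observation window, or that it must fall at a fixed fraction of the truth. The documents do not support either claim: they give no treatment length, discontinuation rate or transplant rate, and patients with earlier recorded starts can remove the shortfall in the mean. Nor can one say that ordinary Kaplan-Meier is right in every case, since without late entry it errs upward when earlier starters are included.

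Duration is a descriptive example item, no hypothesis is tested, and the rates of hypocalcemia, seizures and infections are unaffected.

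**What to change.** In Sections 13.1.1 and 13.2, state that duration of treatment will be reported as time from cinacalcet start to discontinuation:

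- Use Kaplan-Meier, or cumulative incidence with transplant and death as competing events.
- Censor courses without a stop date at the last date known to be on treatment.
- Enter courses begun before the study window late (left truncation), or show new starters separately.
- Give the number of courses still ongoing at censoring in every report.

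If the plain mean and median are kept, label them *observed on-study treatment time* and still give the number ongoing.

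The cost is a few sentences and one extra table by the registry's analysts, from start, stop and follow-up dates that the plan already uses. The drawback is that the median may not be reached in the year 1 report: no course starting inside a 12-month window can be followed beyond 12 months.
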